9.4 Subject Enrollment, Number and Duration of Subject's Participation

Subjects who have signed the informed consent form (ICF) and comply with all inclusion and exclusion criteria will be enrolled, and undergo treatment at Visit 2 on Day 0. Screening and Baseline may be combined in one visit. If full correction is not achieved after the initial treatment, subjects may receive a touch up treatment 2 weeks later and can receive repeat-treatment (with Princess® Filler Lidocaine only) at Week 36 (Visit 6) or Week 48 (Visit 7) or Visit 7c. Each subject is expected to be in the clinical investigation for a maximum of 104 weeks including the temporary hold on repeat-treatment.

CPH-301-201200F

Approximately 300 subjects will be screened in the USA; the enrollment of a total of approximately 270 subjects is planned in order to obtain at least 240 evaluable subjects randomized in an 1:1 ratio to each clinical investigation group (accounting for a screening failure rate of approximately 10%, as well as approximately 10% of subjects to be excluded from the Per-Protocol Set due to major protocol deviations or subjects lost to follow-up).

The clinical investigation is planned to be conducted at approximately 10-12 US sites with enrolment target of 23-27 subjects per site. Competitive recruitment may be allowed to stimulate enrollment, but no site will be allowed to enroll more than 54 subjects (20%) unless prior approval of the sponsor is given; in this case, the maximum number of subjects per site is capped at 68 (25%). This will maintain adequate balance between the investigational sites.

10

Clinical investigation Procedures and Assessments

10.1 Nasolabial Folds-Severity Rating Scale (NLF-SRS)

The Baseline severity of NLFs will be assessed by the treating investigator in conjunction with the independent blinded evaluating investigator at Screening using the NLF-SRS. Subjects can be included with two fully visible, approximately symmetrical moderate to severe NLFs (same severity) with severity scores of 2 or 3 on the 5- point NLF-SRS for both NLF as judged by the treating investigator in conjunction with the independent blinded evaluating investigator. It is essential that the subject qualifies on both evaluator assessment as having a rating of 2 or 3 on the 5-point NLF-SRS, both investigators do not need to be full agreement as long as they agree that the subject has at rating of 2 or 3. The NLF-SRS is a validated 5-point rating scale ranging from Grade 0 (none) to Grade 4 (extreme) as outlined in Table 1; this scale have been developed and validated by Canfield Scientific Inc. for Croma-Pharma GmbH. Additional information on how NLFs severity should be evaluated for the standardized treating investigator's live assessment and for the standardized live assessment by the independent blinded evaluating investigator will be outlined in the manual.

After enrollment, live assessments, using the NLF-SRS, will be performed by the treating investigator and the independent blinded evaluating investigator (separate assessments) at Week 12 (Visit 4), at Week 24 (Visit 5), at Week 36 (Visit 6) and/or at Week 48 (Visit 7) and/or at Visit 7c.

Photographic assessments using the NLF-SRS will be performed at the end of the clinical investigation by three blinded independent photographic reviewers.

The treating investigator and the independent blinded evaluating investigator will be trained on the 5-point NLF-SRS prior to the study start, during the investigator meeting, a live WebEx with a sponsor medical consultant, or through review of a recording of the WebEx. Additional open questions will be answered during the pre-study visits; further training on the scale will be also performed during site pre-study visits, if needed. The independent blinded photographic reviewers will be trained on the 5-point NLF-SRS prior to their assessments of the photographs.

Table 1: Nasolabial Folds-Severity Rating Scale (NLF-SRS)

Grade	Definition	
0	None/minimal: No visible/minimal NLFs	
1	Mild: shallow but visible nasolabial fold with a slight indentation	
2	Moderate: moderately deep nasolabial fold	
3	Severe: very deep nasolabial fold with prominent facial feature	
4	Extreme: extremely deep and long nasolabial fold with skin redundancy	

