	FILLER Lidocaine or only Juvéderm® Ultra XC) during initial
	treatment will be excluded from the FAS.
	Per-Protocol Set (PPS)
	The Per-Protocol Set (PPS) is defined as a subset of the subjects
	in the Full Analysis Set who had no major protocol deviations.
	Safety Analysis Set (SAF)
	The Safety Analysis Set (SAF) comprises all subjects who were
	randomized and received at least one treatment (i.e., any dose of
	Princess® FILLER Lidocaine or the control medical device).
	The PPS and FAS will be both considered equally important for
	the primary analysis; the primary analysis will be performed with
	the FAS; if Princess® FILLER Lidocaine can be considered non-
	inferior to Juvéderm [®] Ultra XC according to this analysis, the
	sensitivity analysis based on the PPS can be considered
	confirmatory. Otherwise, this analysis has to be considered
	exploratory. Non-inferiority is demonstrated only if the results are
	consistent for both analysis data sets.
	All effectiveness analyses will be conducted for the FAS and
	subsequently for the PPS. Safety analyses will be based on the
	SAF.
	07 H .
General Statistical	The analysis of the primary effectiveness outcome measure using
Considerations	the FAS and the subsequent sensitivity analysis using the PPS, as

well as the analyses of the secondary outcome measures 1 and 2, will be considered confirmatory within the bounds of the corresponding hierarchical testing procedure. All other analyses will be considered exploratory.

Planned Statistical Analysis

All effectiveness outcome measures will be tabulated by treatment group and visit. To calculate the primary outcome measure, the improvement over Baseline in the NLF-SRS grade assessed by the independent blinded evaluating investigator at Week 24 will be computed for each subject and treatment side by subtracting the NLF-SRS grade obtained at Week 24 from ipsilateral NLF-SRS grade obtained at Baseline. The response rate will then be calculated for each treatment group as the proportion of subjects with NLF-SRS improvement (i.e., reduction) of a ≥ 1 point.

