9.2 Inclusion and Exclusion Criteria – Repeat-treatment

9.2.1 Inclusion Criteria

Subjects who meet ALL the following criteria are eligible for a repeat-treatment:

- 1. In the opinion of the treating investigator, the subject has returned to sufficient severity of both NLFs that would have qualified him for enrollment into the clinical investigation initially (note that the subject does not have to return to his Baseline severity to be permitted to receive a repeat treatment)
- 2. Subjects with NLFs with severity scores of 2 or 3 on the 5-point NLF-SRS for both NLFs as judged by the treating investigator in conjunction with the independent blinded evaluating investigator (note that it is not necessary for the treating and evaluating investigator to agree on the same rating)
- 3. Females of childbearing age must have a negative urine pregnancy test at the repeat-treatment visit and must agree to continue to use an adequate method of contraception for the duration of the clinical investigation
- 4. Healthy skin in the nasolabial area and free of diseases that could interfere in cutaneous aging evaluation and/or injection

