- 9 Repeat-treatment at Week 36 (Visit 6) OR Week 48 (Visit 7) OR Post repeat-treatment hold Follow-up (Visit 7c)
- 10 Only if repeat-treatment occurred at Week 36 (Visit 6) OR Week 48 (Visit 7) OR Post repeat-treatment hold Follow-up (Visit 7c)
- 11 All subjects must be asked if they are experiencing or have experienced any signs/symptoms of vision changes or stroke since the injection
- 12 Exclusion criterion based on visual examinations at Baseline
- 13 If a subject was not evaluated for repeat-treatment at Week 36 (Visit 6) and/or Week 48 (Visit 7) due to the hold on repeat-treatment, the subject could attend Visit 7c for evaluation and repeat-treatment (if eligible)
- a Includes information on prior medication, defined as all medication taken/received within the previous ten days
- b Includes date of birth, sex, race and ethnicity
- c Visual examinations (including Snellen visual acuity, confrontational visual fields and ocular motility) to be performed at Baseline and at Week 4; in case of touch-up treatment, to be performed at 4 and 12 weeks after repeat-treatment visit. To be performed prior to- and 30 min after any treatment after all other assessments. The subject should wear the same corrective eyewear (i.e. glasses/contact lenses) at each assessment, if appropriate. The definition of clinically significant changes and action to be taken is presented in Section 10.8.4 of the protocol.
- d In women of childbearing potential only, including those who are postmenopausal for less than twelve months
- e Evaluation and grading of nasolabial folds severity by the treating investigator and by the independent blinded evaluating investigator (separate assessments) will be done using the 5-point NLF-SRS. The Baseline severity is the severity grade assigned at Screening as determined by the treating investigator in conjunction with the independent blinded evaluator. The left and right cheek will be separately evaluated.
- f Clinical photography will be performed; the evaluation and grading of nasolabial folds severity by the independent blinded photographic reviewers using the 5-point NLF-SRS and based on photographs will take place at the end of the clinical investigation. The left and right cheek will be separately evaluated
- g Evaluation of subject satisfaction using the FACE-Q questionnaire "Satisfaction with Outcome"
- h Evaluation of subject appearance appraisal using the FACE-Q questionnaire on "Appraisal of Nasolabial Folds"

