5.1. Primary Effectiveness Endpoint

The estimand for the primary effectiveness endpoint is defined as follows:

- Treatment: Princess® FILLER Lidocaine and Juvéderm® Ultra XC for the treatment of NLF (both sides) in each subject.
- Population: Of all subjects defined by the study inclusion / exclusion criteria, the analysis population will include subjects who were randomized to the study treatment and received both treatments (Princess® FILLER Lidocaine and the control medical device) as initial treatment at the same visit (FAS population).
- Variable: A binary variable indicating the subject is alive and has a NLF-SRS response based on the independent blinded evaluating investigator live assessment using the NLF-SRS at Week 24 after initial treatment and relative to baseline assessments. NLF-SRS responder with regards to each specific NLF is defined as a subject with at least one grade improvement from baseline in NLF-SRS in that NLF.
- Intercurrent events:
 - The intercurrent event 'death' is very unlikely in this study, however, in case of death prior to Week 24, this will be considered as non-response following the composite strategy.
 - Major protocol deviations impacting the NLF-SRS assessment will be handled using the treatment-policy strategy, i.e., the NLF-SRS value at Week 24 will be used for categorization of response.
- Population-level summary: Paired difference of NLF-SRS response rates between Princess® FILLER Lidocaine and the control medical device for non-inferiority comparison.

Study discontinuation (due to any reason) prior to Week 24 is not considered as an intercurrent event, however this will lead to missing Week 24 values, which will be imputed using single imputation strategy as non-response for the primary analysis of this estimand. Subjects with missing NLF-SRS value at Baseline will be considered as non-response for the primary analysis of this estimand.

5.2. Key Secondary Effectiveness Endpoint 1

The estimand for the key secondary effectiveness endpoint 1 is defined as follows:

- Treatment: Princess® FILLER Lidocaine and Juvéderm® Ultra XC for the treatment of NLF (both sides) in each subject.
- Population: Of all subjects defined by the study inclusion / exclusion criteria, the analysis population will include subjects who were randomized to the study treatment and received both treatments (Princess® FILLER Lidocaine and the control medical device) as initial treatment at the same visit (FAS population).

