8.1. Evaluation Methods and Response Rate

8.1.1. Nasolabial Folds (NLF) Severity Rating Scale (NLF-SRS)

NLF-SRS is a five-point scale graded from 0 (None/minimal: No visible wrinkles) to 4 (Extreme: Extremely deep and long fold with skin redundancy) see [Table 3](#). After enrollment, live assessments

This document is confidential.

using the NLF-SRS, will be performed by the treating investigator and the independent blinded evaluating investigator in conjunction at Baseline and as separate assessments at Week 12 (Visit 4), at Week 24 (Visit 5), at Week 36 (Visit 6), at Week 48 (Visit 7) and the post repeat-treatment hold follow-up visit (Visit 7c). Photographic assessments using the NLF-SRS will be performed at the end of the clinical investigation by three blinded independent photographic reviewers. The left and the right NLF will be graded separately.

Table 3 NLF Severity Rating Scale (NLF-SRS)

NLF-SRS grade	Definition
0	None/minimal: No visible/minimal nasolabial folds
1	Mild: shallow but visible nasolabial fold with a slight indentation
2	Moderate: moderately deep nasolabial fold
3	Severe: very deep nasolabial fold with prominent facial feature
4	Extreme: Extremely deep and long nasolabial fold with skin redundancy

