%macro miparams(data=, smin=, smax=, sinc=, outparams=);
ods select none;

data &outparams;
  set _null_;
run;

/*----- # of shift values -----*/

%let ncase= %sysevalf( (&smax-&smin)/&sinc, ceil);

/*---- Multiple imputation analysis for each shift ----*/
%do j=0 %to &ncase;
  %let sj= %sysevalf( &smin + &j * &sinc);

/*---- Generates 100 imputed data sets ----*/

proc mi data=&data seed=12345 nimpute=100 round=1 minimum=0 maximum=4
out=mono;
  class treatment;
  var treatment sex age base week12 week24;
  mcmc impute=monotone;
run;

proc mi data=mono seed=12345 nimpute=1 round=1 minimum=0 maximum=4 out=outmi;
  by _Imputation;
  class treatment;
  var treatment sex age base week12 week24;
  monotone reg;
  mmar adjust( week24 / shift=&sj adjustobs=(treatment='1') );
run;

/*---- Categorization of response in imputed data sets ----*/

data outmi;
  set outmi;
  chg= week24 - base;
  if chg<0 then response=1;
  else response=0;
run;

/*----- Perform genmod test -----*/

ods output parameterestimates=paramest;
proc genmod data=outmi;
```

This document is confidential.

```
    by _Imputation_;
    class id treatment;
    model response (event='1')=treatment/dist=binomial link=identity;
    repeated subject=id;
    lsmeans treatment/diff cl;
    lsmestimate treatment/cl lower testvalue=-0.1 alpha=0.025;
run;

/*----- Combine genmod results -----*/

ods output parameterestimates=miparams;
proc mianalyze data=paramest;
    modeleffects estimate;
    STDERR stderr;
run;

data miparams;
    set miparams;
    Shift= &sj;
    keep Shift Probt;
run;

/*----- Output multiple imputation results -----*/
data &outparams;
    set &outparams miparams;
run;

%end;

ods select all;
%mend miparams;
```

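### Does the primary endpoint fail for want of a rule on whose pre-treatment NLF-SRS grade is the baseline when the two raters split 2 versus 3?

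*Protocol*

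**What the plan says.** Footnote e of the schedule, in the same words in Protocol 2.1 and SAP 2.10, fixes the source of the baseline: "The Baseline severity is the severity grade assigned at Screening as determined by the treating investigator in conjunction with the independent blinded evaluator". SAP 8.1.1 agrees, describing grading by the two investigators "in conjunction at Baseline and as separate assessments at Week 12 (Visit 4), at Week 24 (Visit 5") and later visits.

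Protocol 10.1 allows the two to differ: "both investigators do not need to be full agreement as long as they agree that the subject has at rating of 2 or 3". The repeat-treatment criterion in Protocol 9.2.1 also has the two raters judge in conjunction, and adds "note that it is not necessary for the treating and evaluating investigator to agree on the same rating".

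The response rule in the protocol synopsis names the blinded evaluator for Week 24 and computes improvement by "subtracting the NLF-SRS grade obtained at Week 24 from ipsilateral NLF-SRS grade obtained at Baseline". The SAP 5.1 estimand is "based on the independent blinded evaluating investigator live assessment using the NLF-SRS at Week 24 after initial treatment and relative to baseline assessments". The sample code in SAP 8.4 reads a single baseline variable: "chg= week24 - base".

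Protocol 10.11.2 lists a separate pre-treatment NLF-SRS grade by each rater at Visit 2. The NLF-SRS row of both schedules is marked at Screening and empty at Visit 2. SAP 6.2 gives a general default: the last value before the device, expected on Day 1, with Screening used if Day 1 is unavailable. The default applies only where nothing else is specified.

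**The concern.** The entry criterion confines the baseline to 2 or 3, and response needs one grade. For a subject whose raters split, the choice of grade alone decides response whenever a fold stands at grade 2 at Week 24. This affects the primary endpoint of a pivotal trial and key secondary 2, both of which are in the confirmatory hierarchy.

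Grading in conjunction cannot simply be read as consensus, because Protocol 9.2.1 uses that expression while saying that agreement is not needed. Two programmers could build different baselines and each cite a passage: the joint Screening grade under footnote e, or a Visit 2 grade under SAP 6.2. An unwritten rule could also be settled after results are known. SAP 5.1 adds: "Subjects with missing NLF-SRS value at Baseline will be considered as non-response for the primary analysis of this estimand". A baseline tied to a visit at which the schedule shows no grading could therefore seem to create artificial non-responders.

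**Working it through.** **The plan's own figure.** Inputs from Protocol 14.3: 87% versus 88%, independent folds, margin −10 points, one-sided 95% Newcombe-Wilson interval, 222 subjects, 90% power. A simulation of 200,000 trials gives 88.4% power at n = 222. The plan's figure came from 1,600 simulations, with a standard error of about 0.8 points, so it is reproduced closely enough.

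**Where the choice matters.**

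| Week 24 grade | Baseline 2 | Baseline 3 |
|---|---|---|
| 0 or 1 | responder | responder |
| 2 | non-responder | responder |
| 3 or 4 | non-responder | non-responder |

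Only a split subject with a fold at grade 2 at Week 24 is affected.

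**Both folds at grade 2.** They flip together. Response rates move, but the paired difference and the discordant count do not. Lowering both rates by 3, 5 or 10 points in this way leaves simulated power at n = 222 (one-sided 0.05) at 88.2%, 88.4% and 88.7%.

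**One fold at grade 2, the other at 0 or 1.** Lowering the baseline from 3 to 2 turns a both-fold responder into a control-only responder if the test fold is the one at grade 2. It becomes a test-only responder if the control fold is. The two movements offset.

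To size this, take n = 243 (270 less 10%) and independent folds. Let m be the share of subjects whose subtracted grade is one below the evaluator's own. The documents give neither m nor the two-grade response rates. I assume 30% or 60% on control and, by the same probit shift that separates 87% from 88%, 28.3% or 58.1% on test. With m = 20%, 243 × 0.20 = 48.6 subjects are affected:

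- To control-only: 48.6 × (0.87 − 0.283) × 0.30 = 8.6, or 48.6 × (0.87 − 0.581) × 0.60 = 8.4.
- To test-only: 48.6 × (0.88 − 0.30) × 0.283 = 8.0, or 48.6 × (0.88 − 0.60) × 0.581 = 7.9.
- Net: about half a subject toward control-only.

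Across all cells the expected difference changes by m × [(test − control at two grades) − (−1.0)]. With unrounded test rates of 28.33% and 58.11%, this is 0.20 × (−1.67 + 1.0) = −0.13 points, or 0.20 × (−1.89 + 1.0) = −0.18 points.

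**The visit question.** Footnote e specifies Screening for this scale, so the SAP 6.2 default need not apply. Where the default is used, it already falls back to Screening, so no subject loses a baseline for want of a Visit 2 grade. When Screening and Baseline are one visit, which both schedules allow, the timing conflict disappears.

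**The case for a change.** The strongest opposing case is a fragility count. At 87% versus 88% and n = 243, the independent-fold cells are 0.87 × 0.12 × 243 = 25.4 test-only and 0.88 × 0.13 × 243 = 27.8 control-only. The paired Wald lower limit at one-sided 0.025 (the level in SAP 8.2.1) is −1.0% − 1.96 × √[(0.2188 − 0.0001)/243] = −6.9%. Moving subjects one at a time from both-respond to control-only brings the limit past −10% at the seventh (−10.1%), or at the ninth if the folds have a latent correlation of 0.5. Seven of 243 is 2.9%, which sounds alarming.

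That count runs in one direction only, so the seven must be a net excess. Under the assumptions above, the chance that the two streams of movers net seven or more toward control-only is 0.1% at m = 5%, about 1.5% at m = 10% and about 7% at m = 20%.

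A mismatch that always runs one way does change power. At m = 10% it goes from 85% to 80–81% if the subtracted grade is always one below, and to 89% if always one above. A balanced mixture leaves it at about 85%. Nothing in the documents points to a systematic direction.

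With a true difference of −10 points on the evaluator's own scale and m = 10%, the chance of passing is 5.3% when the subtracted grade is always above, against 2.7% with no mismatch. But the difference on the subtracted scale is then −9.0 points. This is an error rate only if the evaluator's own grade is declared the true scale, and the plan does not declare that.

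Two parts of the objection stand. Neither document states how a permitted split becomes one grade, although the rating manual and the table shells, which are not in the file, may do so. And Protocol 10.11.2 disagrees with footnote e and both schedules.

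**Conclusion.** The gap is one of wording, and no change to the plan follows. Footnote e and SAP 8.1.1 already give analysts a workable baseline, the joint Screening grade. The same-severity criterion (Protocol 9.1.1, SAP 2.6.1) means the choice normally applies to both folds. Protocol 10.9 allows randomization only after eligibility is confirmed, so that grade cannot depend on which side receives which device. The within-subject comparison is sound under any pre-treatment rule applied alike to both sides. What the choice mainly moves is the level of both response rates.

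The obvious alternative is the evaluator's own grade where recorded, with the joint grade otherwise. It would put the same blinded rater at both ends, but it mixes baseline sources across subjects, and its fallback is undefined for exactly the split subjects at issue. No gain has been shown for it. The Visit 2 entries in Protocol 10.11.2 are a documentary inconsistency.

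The expected effect on the paired difference is 0.13 to 0.18 points even with 20% of subjects mismatched in one direction. That figure rests on independent folds and assumed two-grade response rates. The actual share of split grades is unknown. A large mismatch running in one direction would cost some power, but it would give neither device a built-in advantage.

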10.2 Global Aesthetic Improvement Scale (GAIS)

The GAIS is a 5-point scale that rates global aesthetic improvement from the pre-treatment appearance. The ratings are "worse", "no change", "improved", "much improved", and "very much improved" and will be judged by the evaluating investigator (Table 2). Additional information will be available in manuals for independent blinded evaluating investigators and for subjects.

The GAIS assessment will be performed separately by the independent blinded evaluating investigator and the subject at Week 12 (Visit 4), at Week 24 (Visit 5), at Week 36 (Visit 6), at

Week 48 (Visit 7) and/or at Visit 7c. At Week 36 (Visit 6), Week 48 (Visit 7), and/or Visit 7c,

GAIS assessments will be performed prior to repeat-treatment.

Separate assessments will be performed for the left and the right side of the face.

Table 2: Global Aesthetic Improvement Scale

Grade		Definition
1	Very much improved	Optimal aesthetic results for the implant in this subject
2	Much improved	Marked improvement in appearance from initial condition, but not completely optimal for this subject. A touch-up would slightly improve the result
3	Improved	Obvious improvement in appearance from the clinical condition, but a touch-up or retreatment is indicated
4	No change	The appearance is essentially the same as the original condition
5	Worse	The appearance is worse than the original condition

Cited from (Narins et al., 2003).

